Survey of providers: We will conduct a survey of primary care providers to assess the impact of the intervention on staff with measures described below to understand implementation issues. The survey will be conducted at baseline and following the 3-year intervention, using a mixed approach, including hard copies, in person or in office mailboxes, and email. In our previous study, we had a 65% response rate from providers and nurses, and we anticipate a similar response rate in the proposed study. A statement will be included with the survey outlining the number of times the survey will be conducted (2) and the timeframe for the surveys.

Semi-structured interviews: To further understand the clinic staff's lived experience of the CHW intervention, we will conduct brief, semi-structured interviews of the providers at baseline and semi-annually, for a total of 6 times (baseline, and after years 1, 1.5, 2, 2.5, and 3) with a subset of participating PCPs identified as key informants based on their experience and institutional knowledge. To understand any changes in how teams collectively integrate CHWs into their practices, we will also conduct brief, semi-structured interviews with primary care team members other than providers at the same intervals. Through these surveys and interviews, we will assess key aspects of the implementation of the CHW intervention as experienced and perceived by clinic staff. To additionally understand factors that impede or facilitate the implementation of the intervention, we will conduct semi-structured interviews annually (after years 1, 2, and 3) with practice administrators at each health care organization; key informants knowledgeable about population health and health policy at city level as relevant to DM prevention; and staff at the nutrition and exercise programs, whose involvement in the program can enable implementation success. Interviews will continue until emerging themes are saturated, anticipating up to 25 subjects at each site (approximately 20 involved in primary care delivery, 2 in managerial or administrative roles, and up to 3 staff at nutrition and exercise programs) and up to 5 informants outside the two sites who can speak to macro-level factors. These interviews will be audio-recorded and transcribed for analysis.

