provider has switched teams, newly enrolled patients attributed to this provider will enter the study in their provider's current study arm. For the intervention group, CHWs will contact patients when they are due for PC visits to ensure that they complete regular screenings as one of the toolkit strategies. Loss to follow-up of patients assigned to control teams is a concern, however we will address it through data reports provided to the control teams, which will include patients due for an HbA1c screening.

To limit bias due to contamination and missing values, we will assess the baseline characteristics of patients who switch teams or are removed from the panel or have incomplete repeated outcomes, and compare them with that of the other participants. The (generalized) linear mixed-effect models discussed earlier can deal with attribution problem and other missing data automatically, under the missing-at-random assumption. This model assumes that the missing information only depends on the observed information, which allows us to utilize all the observed information. To better understand the nature of our missing data and its mechanism; we will summarize the outcome variables by discontinuation status/reason in each arm. If the trajectories of the primary outcome variables from those with incomplete data are similar to those with complete information, the data may be missing at random; otherwise, it may be missing not at random. We will then conduct sensitivity analysis to assess the impact of missing not at random data on our analysis. The sensitivity analysis will test whether our primary statistical analysis remains credible if we investigate cases where those patients with incomplete data have outcomes that are unfavorable to the intervention arm of the study (e.g. those with incomplete outcome data in the control arm are less likely to develop DM, lose weight or have improved glycemic control or that those with incomplete outcome data in the intervention group are less likely to have lost weight or improved glycemic control but more likely to have developed DM). The sensitivity analysis will be conducted via multiple imputation using sequential modeling, applying a SAS macro.

Analysis: Intervention Implementation

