Staff survey data will be used to assess the self-efficacy and collective-efficacy as a team in preventing DM and in working with a CHW coach. We will compare baseline and post-intervention scores on each of the measures. To test the hypothesis that staff assigned to the intervention teams who work closely with a CHW will improve their self and collective efficacy of DM prevention and CHW coaching, we will compare post-intervention scores for these measures across the study arms using linear regression and controlling for baseline scores and adjusting for staff roles, length of time in their role and site. Survey data will also be used to assess PCPs' readiness to work with CHWs for DM prevention. Baseline and post-intervention scores will be compared using Wilcoxon signed-rank tests.

All interviews transcripts (from PCMH and other staff, practice administrators, CHWs, and key informants) and observations of study team meetings and case conferences will be analyzed for common themes by two independent researchers for qualitative analysis. First, two researchers will read the transcripts to identify key domains. Second, the researchers will independently code two of each set of transcripts. They will then meet to develop initial codebooks with code names and meanings. Third, each coder will apply the codebook to the remaining transcripts. Fourth, coders will meet to compare codes and identify patterns and common themes throughout the transcripts. Baseline interviews will be used to guide toolkit refinement and to explore anticipated facilitators and barriers to incorporating CHWs into the PCMH workflow. Mid- and post-intervention interview data will help us to determine key barriers, facilitators and lessons learned from staff, CHWs, and key informants regarding the implementation of CHWs in PC practice.

To assess implementation fidelity, baseline and 6-monthly scores on the coverage, duration, and frequency of CHW-patient contact for BH and VA patients will be compared using ANCOVA. Content of delivery will also be assessed qualitatively based on a sample of CHW-patient contacts. Implementation fidelity will be compared across BH and the VA to examine if differences in organizational setting shape the implementation process.

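### The staff-efficacy regression has no rule for staff without a baseline score and by default drops their post-intervention answers; one two-round mixed model would keep them at little cost.

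*Combined protocol and SAP*

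**What the plan says.** Under Implementation Research, the survey of providers has two rounds: "The survey will be conducted at baseline and following the 3-year intervention". On response it says "we had a 65% response rate from providers and nurses, and we anticipate a similar response rate in the proposed study". It does not say whether 65% applies to each round or to staff completing both.

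Under Analysis: Intervention Implementation, the hypothesis that working with a CHW raises staff efficacy is tested between the randomised arms: "we will compare post-intervention scores for these measures across the study arms using linear regression and controlling for baseline scores". Role, tenure and site enter as further covariates. No sentence says what happens to staff with only one of the two scores.

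The attrition and missing-data paragraphs sit under Analysis: Patient Clinical Outcomes and Health Behaviors. There the plan states "we will assess the baseline characteristics of patients who switch teams or are removed from the panel or have incomplete repeated outcomes", relies on the patient-outcome mixed models under missing-at-random, and adds a sensitivity analysis for unfavourable patient outcomes: "The sensitivity analysis will be conducted via multiple imputation using sequential modeling, applying a SAS macro". None of this mentions staff scores.

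**The concern.** A regression with the baseline score as a covariate needs that score for every person it uses. Standard software omits a record with a missing covariate, so a staff member who was randomised with their team and supplied the outcome, but missed the baseline survey, would leave the analysis. With three years between rounds and incomplete response expected, that group could be sizeable.

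At stake is the precision of a randomised comparison that has little data to spare: the section on number of subjects lists 12 VA and 4 Bellevue teams, so at most 16 clusters. The analysed staff would also be narrower than the staff who were randomised. The plan already values using all observed information for patient outcomes, but does not carry that over to the staff survey.

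**Working it through.** **The plan's own figure.** 65% is an input carried over from an earlier study. The plan gives no staff sample size, power or both-rounds figure, so there is nothing to reproduce.

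**Inputs.** From the plan: p = 0.65, read as response per round; two rounds, three years apart; regression on baseline score. Not in the plan, so assumed: dependence between rounds (phi, the correlation between answering round 1 and answering round 2), turnover, baseline-to-post correlation (rho), staff per team and team ICC.

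**Share of staff with both scores.**
- Independent rounds: p × p = 0.65 × 0.65 = 0.4225, about 42%.
- Arithmetic bounds: 2p − 1 = 0.30 to p = 0.65.
- Positive dependence, p² + phi × p(1 − p): phi 0.25 gives 0.479; phi 0.5 gives 0.536.
- Turnover t with independent rounds, 0.4225 × (1 − t): t = 10%, 20%, 30%, 40% gives 38%, 34%, 30%, 25% of the baseline staff.

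**Post-intervention answers without a baseline score**, p − P(both).
- Independent rounds: 0.65 − 0.4225 = 0.2275 of staff, which is 0.2275/0.65 = 35% of post-intervention respondents.
- Identical responders: 0.

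**Gain from using them, no clustering.** With the post-score variance set to 1, information on the arm effect is proportional to P(both)/(1 − rho²) from paired staff, plus P(post only) from the rest. The variance ratio is the first term over the sum.
- rho 0.4: 0.4225/0.84 = 0.503; 0.503/(0.503 + 0.2275) = 0.69, a 31% reduction (SE 17% lower).
- rho 0.6: 0.4225/0.64 = 0.660; 0.660/(0.660 + 0.2275) = 0.74, a 26% reduction (SE 14% lower).
- phi 0.25: reduction 19% to 23%. phi 0.5: 12% to 15%. Identical responders: nil.

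**Gain with team clustering.** Assume 10 staff per team, independent rounds, team variance equal to the ICC and within-team variance w = 1 − ICC, of which baseline explains rho². Variance per team:
- paired staff only: ICC + w(1 − rho²)/4.225;
- all post answers: ICC + 1/[4.225/(w(1 − rho²)) + 2.275/w].

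| ICC | rho | Paired only | All post answers | Reduction |
|---|---|---|---|---|
| 0.1 | 0.4 | 0.279 | 0.223 | 20% |
| 0.1 | 0.6 | 0.236 | 0.201 | 15% |
| 0.2 | 0.4 | 0.359 | 0.310 | 14% |
| 0.2 | 0.6 | 0.321 | 0.290 | 10% |

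Extra respondents in the same teams do not reduce between-team variance, so the gain falls to roughly 10% to 20%.

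**The case against.** Baseline-adjusted regression is a standard choice for a two-round randomised comparison. The plan does not prescribe a complete-case analysis; it is silent, and exclusion is inferred from how such a model is normally fitted. That stands, but the silence is the gap: run as written, with no further rule, the model excludes these staff.

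A reader might take 42% as a floor. It is not: it is the value for independent rounds, with arithmetic bounds of 30% to 65% before turnover. A reader might also infer that the test rests on a long-tenured, highly engaged minority. The documents give no tenure, turnover or engagement data to show that. The two harms also pull against each other: if engagement drives response, the same staff tend to answer both rounds, the paired share rises (54% at phi 0.5) and fewer answers are lost.

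It would also be tempting to call the mixed model's assumption the weaker one. It is not. Complete-case regression tolerates a missing baseline that depends on the baseline score itself, as when low-efficacy staff skip the first survey, provided it does not depend on the outcome given the covariates. Missing-at-random fails there. Neither assumption contains the other.

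Finally, most non-response stays out of reach: staff who left or skipped the second survey still have no outcome. This too stands and limits what the change can claim.

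**Conclusion.** The point holds as a cheap improvement of low severity. The planned regression needs a baseline score, no missing-data provision covers staff, and by default some randomised staff who supplied the outcome would be left out.

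The size is conditional. The 42% paired share and the 35% of post-intervention answers lost require 65% to be per round and the rounds to be independent. The 26% to 31% variance reduction further requires rho of 0.4 to 0.6 and no clustering; the clustered 10% to 20% is the more realistic figure for team-randomised staff, though its ICC and team size are also assumed. If responders are identical, or 65% already describes both rounds, the loss is close to nil. Bias from selection is possible but not demonstrated.

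**What to change.** Analyse all originally randomised staff with either survey, by the arm of the team they were randomised with, in one mixed model covering both rounds: random effects for staff and team, a common baseline mean across arms, arm by time as the effect of interest, adjusted for role, time in role and site. The arm rule needs stating because the plan foresees providers changing arms but settles only how their patients are handled. The precision gain comes from the post-only answers.

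Keep the planned paired regression as a sensitivity analysis. Report by arm how many staff have both scores, and say whether 65% is per round.

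The cost is SAP wording; no new data are needed. The downside is reliance on missing-at-random, an assumption different from that of the paired analysis, which is why both should be reported.

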The goal of this proposal study is to develop and test a model of CHW health coaching, designed to prevent the onset of Type 2 DM in a large population of underserved patients at risk. CHWs will be recruited from the target populations and trained in core competencies to serve as peer health coaches. Our central premise is that CHWs are uniquely suited to engage fellow patients by encouraging lifestyle change through shared experiences and social support to extend the reach of primary care (PC) beyond the clinic visit. This study will test a scalable model of peer health coaching to address the millions of patients at risk for DM, using low cost, culturally congruent personnel to promote prevention of DM in PCMH practice.

Background

Type 2 DM is a preventable chronic disease that affects 11% of US adults. An additional 35% (79 million) have pre-DM and thus at risk of developing DM and cardiovascular disease. DM is a leading cause of death in the US and a major cause of heart disease and stroke. It is essential that the US leverage prevention strategies to mitigate the health and economic impact of DM in the population. Up to 20% of adult PC patients at BH and 25% of veterans at NY Harbor have DM, 2x and 3x the rate in the general population, respectively, and this rate has been steadily increasing. There is also a substantial population with undiagnosed pre-DM, half of who are expected to develop DM in the next decade. Our preliminary analysis of VA NY Harbor data from 2010-2012 showed that 9,610 (62%) of 15,500 veterans <75 years old, without DM, had a glycosylated hemoglobin (HbA1c) test, and 1,730 (18%) of them had pre-DM.

Study Design

We will conduct a cluster-randomized trial to test the impact of peer health coaches on prediabetic patients cared for by PCMH teams at BHC and VA to:

1. Reduce the incidence of type 2 DM in pre-diabetic, PCMH patients;
2. Promote weight loss among pre-diabetic patients;
3. Increase patient activation levels, a measureable construct of engagement, efficacy, skills, and confidence in managing one's health, among pre-DM patients, resulting in:
 - a. Improved secondary clinical outcomes: better glycemic and blood pressure control, and lower Framingham risk scores;

- b. Increased utilization of preventive services (e.g. MOVE!, TeleMOVE!, Healthy Lifestyles, etc.);
- c. Improved health behaviors (e.g. making dietary and exercise changes); and

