- 4. Develop, implement and assess strategies to recruit, train, and integrate peer CHW health coaches within the PCMH model.

The 36-month intervention will be conducted using a staggered entry design across four, overlapping, 12-month waves to account for CHW caseload limits. This study will test a scalable model of peer health coaching to address the millions of patients at risk for DM, using low cost, culturally congruent personnel to promote prevention of DM in PCMH practice. If successful, our study team will work with VA's Central Office and NY City's Health and Hospital Corporation to translate the model for larger scale implementation.

Characteristics of the Research Population

Number of Subjects

All 12 PC teams at VA NY Harbor and all 4 PCMH teams at BH will be eligible to participate. In our VA PROVE study, 51/52 PCPs participated in the intervention, and we expect similar rates in this project. Eligible patients will be identified through the study's pre-DM registry, which will be based on the EMR and Corporate Data Warehouse (CDW) at each site. This methodology builds on our ongoing national, retrospective cohort study of predictors of DM among veterans with pre-DM back to 2008. Based on preliminary analysis of VA NYHHS data from 2010-2012, 62% of veterans enrolled in PC without DM, have had an HbA1c test in the previous two years.

In the intervention group, we anticipate contacting 2,100 randomly selected patients (1,050 at the VA* and 1,050 at BH) to ultimately enroll about 1,100 patients (550 at the VA and 550 at BH). This outreach sample reflects our assumption that 20% of patients will be unreachable and that 60% of those reached will enroll in the study. Another 1,100 patients attributed to control group providers will be randomly selected as the control group, in accordance with the waiver of HIPAA authorization. As detailed below, the control group will not participate in the CHW intervention. The total sample, including the intervention and control groups, will be about 2,200 patients. This amounts to approximately 265 patients (across intervention and control groups) per wave and per clinical site.

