To assess the overall effectiveness of the CHW intervention we will compare cumulative DM incidence rates and time to DM incidence (in addition to other outcomes: weight loss, obesity rate, and health care utilization) between the two study groups, using intention-to-treat and per protocol analyses. Time to DM incidence at 12-month follow-up of the intervention and control arms, aggregated across the 4 study waves, will be compared using Cox proportional hazard regression models. Chi-square analyses will be conducted to compare outcomes between the two groups for categorical variables (e.g. obesity rate, PAM stage) and t-tests will be conducted for continuous outcomes (e.g. weight change, PAM score). We will then conduct (generalized) linear mixed-effects modeling, which will (1) take into account the intra-cluster correlation coefficient (ICC) of patients within providers and teams, (2) analyze repeated measures at several time-points (baseline, midpoint, and post-intervention) simultaneously, (3) include team or patient level baseline covariates easily, if they are found to be unbalanced between two arms, and (4) deal with attrition problems and other missing data automatically. For categorical outcomes, such analyses will be implemented using SAS Proc GLIMMIX, while using SAS Proc MIXED for continuous outcomes.

We will use multilevel survival analysis to determine the effect of the intervention on time to DM, as patients are enrolled in waves and the time to DM incidence may be censored by the end of study. Specifically, we will fit Cox proportional hazard regression models with mixed effects to examine the hazard ratio between two groups, adjusting for important covariates and taking into account the correlation among patients within teams.

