All primary care staff will be given information about the proposed research during regular staff meetings, email announcements and a study flyer and then asked to participate. Staff providing verbal consent to participate will be randomized (as part of their PACT team) to either work with a CHW or serve as controls. Staff who opt-out will not be randomized, although might still work on a team that is included in the study. For example, if one primary care provider in a team declines participation, the other providers and team members consent, the team will be randomized to a study arm. If that team is randomized to an intervention arm, the

CHW would only work with the patients of the consenting providers. We anticipate that we will be able to obtain sufficient numbers of staff consenting to participate, as in our previous panel management study only one PCP out of fifty-one declined, and a majority of staff reported that the interventions and CHW support were helpful. Lastly, as CHWs will be extending services and interventions that are a part of regular, evidence-based practice on behalf of patients' primary care physician, patients will not individually consent to receiving phone calls, mailings, or any other contact with the CHW. For surveys, which are research procedures specific to this study, consenting elements will be presented at the top of the survey. Primary care teams will pre-approve all lists of patients receiving interventions as well as approving the content of the CHW's intervention. Patients will have the right to opt out of receiving outreach at any time. All mail materials will include instructions on how to stop receiving mail from the CHW.

A waiver of authorization for both recruitment/identification purposes and for study procedures has been sought. We use the electronic medical record to generate a list of eligible participants, in order to approach them to screen for eligibility. Without the requested Waiver, screening could not be practically carried out and would adversely affect the scientific rigor of the study.

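### The staff-efficacy comparison makes no stated allowance for team, although staff are randomised by team; if within-team correlation remains, the 5% test is anti-conservative

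*Combined protocol and SAP*

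**What the plan says.** Study Design describes the trial as cluster-randomised: "We will conduct a cluster-randomized trial to test the impact of peer health coaches". The section on subject identification, recruitment and consent says that consenting staff "will be randomized (as part of their PACT team) to either work with a CHW or serve as controls". Number of Subjects limits the clusters: "All 12 PC teams at VA NY Harbor and all 4 PCMH teams at BH will be eligible to participate", so there are at most 12 + 4 = 16.

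Analysis: Intervention Implementation uses the staff survey to "assess the self-efficacy and collective-efficacy as a team in preventing DM" and in working with a CHW coach. It states a hypothesis that staff on intervention teams will improve. For the test, "we will compare post-intervention scores for these measures across the study arms using linear regression", "controlling for baseline scores and adjusting for staff roles, length of time in their role and site". Team is not among the listed terms. No random effect, cluster-robust standard error or team-level analysis is named.

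Elsewhere the plan does name methods for clustering. The mixed models under Analysis: Patient Clinical Outcomes and Health Behaviors "take into account the intra-cluster correlation coefficient (ICC) of patients within providers and teams", and the Cox models there allow for correlation within teams. The neighbourhood analysis nests patients within neighbourhoods. None of these is extended to the staff survey.

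**The concern.** This is a hypothesis test between randomised arms in which the randomised unit is the team and the analysed unit is the staff member. Colleagues on a team share leadership, workload, a patient panel and, in the intervention arm, a CHW. Collective efficacy is by definition a judgement about the team. Two responses from one team are therefore likely to carry less information about the arm effect than two responses from different teams. A regression that counts every respondent as a separate unit understates the uncertainty.

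The listed covariates do not close the gap. Site has two levels and cannot absorb differences among 16 teams. Role and time in role vary within teams. Baseline adjustment may lower the residual correlation but does not in general remove it.

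At stake is a claim that working with a CHW raises staff efficacy when the difference seen is ordinary variation between teams. That claim would inform the fourth aim, on integrating CHWs into the medical home, and the plan intends wider implementation if the study succeeds.

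**Working it through.** **No figure to reproduce.** Statistical Power and Sample Size gives no sample size, power or ICC for the staff test. The question is how far the true error of a nominal 5% test moves if team is left out.

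**Inputs from the documents:** at most 16 teams (12 VA, 4 BH), allocation by team, and a staff model with arm, baseline score, role, time in role and site.

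**Assumptions:** equal split (8 teams per arm; 6/6 at the VA and 2/2 at BH); m = 3, 5 or 8 responding staff per team, equal across teams; residual ICC from 0.01 to 0.30; two-sided 5% level (the plan states 0.05 only for patient time-to-event power, without sidedness).

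**Formulas.** Design effect DE = 1 + (m - 1) x ICC. The ratio of naive to true standard error is 1/sqrt(DE). True error = 2 x [1 - Phi(1.96/sqrt(DE))].

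**Worked example,** m = 8, ICC 0.10: DE = 1 + 7 x 0.10 = 1.70; 1/sqrt(1.70) = 0.767; 1.96 x 0.767 = 1.503; true error = 13.3%.

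**Check by simulation.** 10,000 null trials per cell, 16 teams, linear regression on arm, baseline and site without a team term. Role and time in role were not simulated.

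| m | ICC | DE | SE ratio | True error, formula | True error, simulated |
|---|---|---|---|---|---|
| 3 | 0.01 | 1.02 | 0.990 | 5.2% | 5.3% |
| 3 | 0.05 | 1.10 | 0.953 | 6.2% | 6.2% |
| 3 | 0.10 | 1.20 | 0.913 | 7.4% | 7.4% |
| 3 | 0.30 | 1.60 | 0.791 | 12.1% | 12.6% |
| 5 | 0.01 | 1.04 | 0.981 | 5.5% | 5.6% |
| 5 | 0.05 | 1.20 | 0.913 | 7.4% | 7.4% |
| 5 | 0.10 | 1.40 | 0.845 | 9.8% | 10.4% |
| 5 | 0.30 | 2.20 | 0.674 | 18.6% | 19.3% |
| 8 | 0.01 | 1.07 | 0.967 | 5.8% | 5.7% |
| 8 | 0.05 | 1.35 | 0.861 | 9.2% | 9.3% |
| 8 | 0.10 | 1.70 | 0.767 | 13.3% | 13.4% |
| 8 | 0.30 | 3.10 | 0.568 | 26.6% | 27.4% |

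At ICC 0 there is no inflation (formula 5.0%; simulated 4.3% to 5.1%).

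**Baseline scores that also cluster by team.** The table treats the ICC as what remains after adjustment. If instead baseline and follow-up each have a team component (m = 8, ICC 0.10, individual correlation 0.5 assumed), the error was about 17%, 13% or 10% when the team effects at the two times correlated 0, 0.5 or 0.8. Baseline adjustment moves the figure but does not restore 5%.

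**After the fix.** Analysing 16 baseline-adjusted team means on arm and site, with t on 16 - 3 = 13 degrees of freedom, gave a simulated error of 4.4% to 5.4% over the same team sizes and ICC from 0 to 0.30. The baseline slope was taken as known in this check.

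**The case against.** The strongest case is that the plan is silent rather than wrong. It says linear regression and lists covariates; it does not say that staff are treated as independent or how standard errors are formed. A reader might infer that ordinary least squares with independent errors has been prespecified. The text does not go that far, since an analyst could attach cluster-robust errors and still call the model linear regression. This stands as a limit on the wording. It does not remove the point: followed as written, the plan adds no allowance for team, and uncorrected robust errors are unreliable with only 16 clusters.

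Second, the effect may be small. Implementation Research describes a survey of primary care providers with about 65% response expected, and a baseline-adjusted model needs both surveys, so respondents per team could be few. The mention of nurses in the earlier response rate and the adjustment for staff roles suggest a wider group. The number is unknown. With 3 per team and ICC 0.01 the error is about 5%, which is trivial. This stands too, and it is why the size is given as a range.

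Third, collective efficacy might be scored once per team, in which case correlation between colleagues would not arise for that measure. The individual-level covariates make this unlikely, and it would not cover self-efficacy.

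Fourth, the test is not primary. That is correct. A reader might infer that the fourth aim turns on this regression, or that the trial's main result is exposed. Neither follows. The aim is also served by interviews, process indicators and fidelity measures, and the patient analyses have their own provision for clustering.

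**Conclusion.** The concern holds in conditional form. The plan randomises staff by team and tests a staff hypothesis between arms with no stated allowance for team. If residual within-team correlation is positive, the standard error is too small and the nominal 5% test is anti-conservative. The direction follows from the design; the size cannot be fixed from the documents. Under the assumptions above, it lies between negligible (about 5-6% at ICC 0.01) and serious (about 27% with 8 per team at ICC 0.30), with about 9-14% at 8 per team and ICC 0.05-0.10. The statement that the test is certainly inflated by a known amount is not supported, because the documents give no ICC, team size or split. The diabetes-incidence analysis is unaffected. The change should be made because the gap is clear and the remedy is cheap.

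**What to change.** In Analysis: Intervention Implementation, replace the linear regression with a linear mixed model that keeps arm, baseline score, staff role, time in role and site, and adds a random intercept for team with Kenward-Roger degrees of freedom. SAS Proc MIXED, already named for continuous patient outcomes, fits this with a RANDOM statement and a degrees-of-freedom option. An acceptable alternative is to analyse baseline-adjusted team means on arm and site. State which is used, and report the number of teams and respondents per team and the estimated ICC. A separate team-level analysis of collective efficacy is not required if the random intercept is used.

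No new data are needed, since team membership is fixed by the randomisation. The cost is width. At 8 per team and ICC 0.10, the standard error grows by sqrt(1.70) = 1.30 relative to the uncorrected regression. With no within-team correlation, the team-mean analysis still widens the interval by about 9%, from the critical value alone (2.16 on 13 degrees of freedom against 1.98 on 124). Those wider intervals are the valid ones for a comparison of at most 16 teams.
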